13. APPENDICES

APPENDIX 1. SAFETY DEFINITIONS AND ASSESSMENTS

Adverse Event (AE)

An AE is defined as any untoward medical occurrence associated with the use of a drug in humans, whether or not considered drug related. An AE can therefore be any unfavorable and unintended sign (including an abnormal laboratory finding, for example), symptom, or disease temporally associated with the use of a medicinal (investigational) product, whether or not related to the medicinal (investigational) products.

Pre-existing diseases or conditions will not be considered AEs unless there is an increase in the frequency or severity, or a change in the quality, of the disease or condition. Worsening of a pre-existing condition is considered an AE.

Any abnormal laboratory test results (hematology, clinical chemistry, or urine) or other safety assessments (eg, vital sign measurements), including those that worsen from screening/baseline that are felt to be clinically significant in the medical and scientific judgment of the Investigator are to be recorded as AEs.

Treatment-emergent AE (TEAE)

A TEAE is defined as any AE not present prior to the initiation of the drug treatment or any AE already present that worsens in either intensity or frequency following exposure to the drug treatment.

Serious Adverse Event (SAE)

An SAE is an AE that meets any of the following criteria in the view of either the Investigator or Ultragenyx:

- Death
- Life-threatening
 - *A life-threatening AE is an event that places the patient or subject at immediate risk of death. It does not include events that if it had occurred in a more serious or severe form might have caused death. For example, drug induced hepatitis that resolved without evidence of hepatic failure would not be considered life threatening even though drug induced hepatitis can be fatal.*
- Inpatient hospitalization or prolongation of existing hospitalization
 - *Hospitalization is defined by Ultragenyx as a full admission to hospital for a period of 24 hours or longer for diagnosis and treatment. This includes prolongation of an existing inpatient hospitalization. Examples of visits to a hospital facility that do not meet the serious criteria for hospitalization include:*
 - *Emergency room visits (that do not result in a full hospital admission)*
 - *Preplanned or elective procedures prior to study enrollment (eg, outpatient surgery)*
 - *Protocol procedures*

- *Hospitalization signifies that the subject has been detained (usually involving at least an overnight stay) at the hospital or emergency ward for observation and/or treatment that would not have been appropriate in the physician's office or outpatient setting. When in doubt as to whether 'hospitalization' occurred or was necessary, the AE should be considered serious.*
 - *AEs requiring hospitalization should be considered SAEs. Hospitalization planned prior to study enrollment (eg, for elective surgery or routine clinical procedures) that are not the result of AE (eg, elective surgery for a pre-existing condition that has not worsened) need not be considered AEs or SAEs. If anything untoward is reported during the procedure, that occurrence must be reported as an AE, either 'serious' or 'non-serious' according to seriousness criteria described above.*
- Disability/Incapacity
 - *An AE is disabling or incapacitating if it results in substantial and/or permanent disruption of the subject's ability to carry out normal life functions.*
- Congenital anomaly/birth defect not present at screening
- Important Medical Events that may not result in death, be immediately life-threatening, or require hospitalization may be considered serious when, based upon appropriate medical judgment, they may jeopardize the patient or subject and may require medical or surgical intervention to prevent one of the criteria listed in the definition. Examples of such events are:
 - Intensive treatment in an emergency room or at home for allergic bronchospasm
 - Blood dyscrasias that do not result in inpatient hospitalization
 - Development of drug dependency or drug abuse
 - Emergency room visits requiring medical intervention related to the study or study procedures, where subjects, due to hospital capacity, could not be admitted (eg, due to coronavirus 2019 [COVID-19])

Participation-emergent Adverse Events

These events may be related to study participation or biological specimen collection and will be reported by the Investigator and noted as such in the case report form (CRF) as related to study intervention.

Overdose

An overdose is defined as a known deliberate or accidental administration of investigational drug, to or by a study subject, at a dose above that which is assigned to that individual subject according to the study protocol. All cases of overdose (with or without associated AEs) will be documented in the CRF.

Assessment of Severity

The severity or intensity of an AE refers to the extent to which an AE affects the patient's daily activities. The severity of all AEs will be graded using the Common Terminology Criteria for

Adverse Events (CTCAE) version 5.0, published on November 27, 2017, unless the AE is Cytokine Release Syndrome (CRS), in which case the AE will be graded by the American Society for Transplantation and Cellular Therapy (ASTCT) Consensus Grading for CRS (Lee et al., 2019).

Table 13: American Society for Transplantation and Cellular Therapy Consensus Grading for Cytokine Release Syndrome

CRS Parameter	Grade 1	Grade 2	Grade 3	Grade 4
Fever ^a	Temperature $\geq 38^{\circ}\text{C}$	Temperature $\geq 38^{\circ}\text{C}$	Temperature $\geq 38^{\circ}\text{C}$	Temperature $\geq 38^{\circ}\text{C}$
		with		
Hypotension	None	Not requiring vasopressors	Requiring a vasopressor with or without vasopressin	Requiring multiple vasopressors (excluding vasopressin)
		And/or ^b		
Hypoxia	None	Requiring low-flow nasal cannula ^c or blow-by	Requiring high-flow nasal cannula ^c , facemask, nonrebreather mask, or Venturi mask	Requiring positive pressure (eg, CPAP, BiPAP, intubation and mechanical ventilation)

^a Fever is defined as temperature $\geq 38^{\circ}\text{C}$ not attributable to any other cause. In patients who have CRS then receive antipyretic or anticytokine therapy such as tocilizumab or steroids, fever is no longer required to grade subsequent CRS severity. In this case, CRS grading is driven by hypotension and/or hypoxia.

^b CRS grade is determined by the more severe event: hypotension or hypoxia not attributable to any other cause. For example, a patient with temperature of 39.5°C , hypotension requiring 1 vasopressor, and hypoxia requiring low-flow nasal cannula is classified as grade 3 CRS.

^c Low-flow nasal cannula is defined as oxygen delivered at ≤ 6 L/minute. Low flow also includes blow-by oxygen delivery, sometimes used in pediatrics. High-flow nasal cannula is defined as oxygen delivered at > 6 L/minute.

Note: Organ toxicities associated with CRS may be graded according to CTCAE v5.0 but they do not influence CRS grading.

BiPAP, bilevel positive airway pressure; CPAP, Continuous positive airway pressure; CRS, cytokine release syndrome; CTCAE, Common Terminology Criteria for Adverse Events.

Source: (Lee et al., 2019).

If an AE cannot be graded using the CTCAE criteria, it should be graded using the following definitions:

- Mild (Grade 1): Subject has awareness of signs or symptoms, but easily tolerated and are of a minor irritant type, causing no loss of time from normal activities. Symptoms do not require therapy or a medical evaluation; signs and symptoms are transient.
- Moderate (Grade 2): Events introduce a low level of inconvenience or concern to the subject and may interfere with daily activities, but are usually improved by simple therapeutic measures; moderate experiences may cause some interference with functioning.
- Severe (Grade 3): Events interrupt the subject's normal daily activities and generally require systemic drug therapy or other treatment; they are usually incapacitating.

- Life-threatening (Grade 4): Events that place the subject at immediate risk of death or are disabling.
- Death (Grade 5): Events that result in death.

Note: The term "severe" is often used to describe the intensity (severity) of a specific event (as in mild, moderate, or severe myocardial infarction); the event itself, however, may be of relatively minor medical significance (such as severe headache). This is not the same as "serious" which is based on subject/event outcome or action criteria and is usually associated with events that pose a threat to a subject's life or functioning. Seriousness (not severity) serves as a guide for defining regulatory reporting obligations.

Assessment of Causality

The Investigator will make a causality assessment about the relationship of each AE to study drug. Treatment-related conditions must be distinguished from disease-related conditions.

The Investigator should determine the causality (relation to the study drug) based on his/her clinical experience and on the information given in the Investigator's Brochure. The causal relationship of all AEs to the study drug will be judged as either related (which includes possibly, probably or definitely related) or not related (which includes unlikely or doubtfully related).

To ensure consistency of AE and SAE causality assessments, Investigators should apply the following general guideline:

- **A related** causal relationship means that there is at least a reasonable possibility that the event is caused by the study drug or the research procedures. There may be a reasonable possibility of a causal relationship between study drug/Investigational Product (IP) and the AE when:
 - The event follows a reasonable temporal sequence post IP administration
 - The event is known to be or could be a response to the IP, based upon pre-clinical or clinical data with the product or similar products
 - The event could not be explained by the subject's primary disease including progression/expression of the disease state, other concurrent or underlying illness, and/or prior/concomitant therapies
 - Positive dechallenge: the event resolves or improves after discontinuation of IP (when this information is available)
 - Positive rechallenge: the event reappears or worsens when dosing with IP is resumed after an interruption (when this information is available)
- **Not related** means there is unlikely to be a reasonable possibility of a causal relationship between the event and study drug/IP or the research procedures, and/or that there is a clear causal relationship between other conditions and the AE. There is not likely to be a reasonable possibility of a causal relationship between study drug/IP and the AE when:

- The event does not follow a reasonable temporal sequence post IP administration
- There are no data with the IP or similar products, suggesting the event occurs or may occur with the IP
- There is a more likely alternative etiology, such as subject's underlying primary disease including disease progression or expression, other concurrent or underlying illness, or prior/concomitant therapies
- Negative de-challenge: the event does not improve after discontinuation of IP (when this information is available)
- Negative re-challenge: the event does not worsen after interruption of IP when dosing is resumed after an interruption (when this information is available)

Note: The Investigator's assessment of causality for individual AEs is part of the study documentation process and will be recorded in the patient's medical record, CRF, and SAE form, if applicable. AEs recorded without the Investigator's assessment of the relationship to study drug will be followed up until causality is assigned.

Suspected Unexpected Serious Adverse Reaction (SUSAR) means a SAE that occurs in a clinical trial subject, which is assessed by the Investigator or Ultragenyx as being serious and unexpected based on Reference Study Information (eg, Investigators Brochure [IB]), and as having a reasonable possibility of a causal relationship with the study drug/IP.

Urgent Safety Measure means any measure taken to protect the subjects of a clinical trial against an immediate hazard to their health or safety.

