5.4.3. Potential Risks for Study Participation

Physical injury associated with study assessments and procedures is also a potential risk. This includes discomfort, bleeding, bruising from phlebotomy and local skin irritation from the continuous glucose monitor (CGM) or electrocardiogram (ECG) electrodes. There is also the potential risk of injury during muscle strength tests.

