8.3.3. Study Stopping Criteria

Study enrollment and any further administration of study drug for subjects already enrolled, will be paused and the DMC and regulatory authorities will be notified if, at any time during the study, any of the criteria listed below occur after UX053 administration:

- Death of a subject
- Any serious TEAE with a severity \geq Grade 3 that is assessed as related to study drug or study procedures by the Investigator or Ultragenyx
- Any TEAE with a severity \geq Grade 3 affecting the cardiopulmonary, renal, or neurological systems, regardless of relationship to study drug, pending a DMC safety review

- Anaphylaxis, as defined by the National Institute of Allergy and Infectious Diseases/Food Allergy and Anaphylaxis Network (NIAID FAAN) criteria ([Table 11](#)), pending a DMC safety review
- Increases in ALT or AST $> 2x$ from Baseline and $> 3x$ the ULN, accompanied by total bilirubin $> 2x$ ULN or INR > 1.5 , without findings of cholestasis (defined as serum ALP activity $< 2x$ ULN) and in the absence of a plausible alternate explanation
- Increases in serum concentrations of ALT or AST $> 2x$ from Baseline and $> 3x$ ULN with the appearance of fatigue, nausea, vomiting, right upper quadrant pain or tenderness, fever, rash, or eosinophilia ($> 5\%$ of total leukocytes)
- 3 subjects develop platelet counts $< 50,000$ per mm³ (or thrombocytopenia \geq Grade 3 in severity)
- 3 subjects develop INR > 1.5 (or INR increase \geq Grade 2 in severity)

In addition to the above criteria, the DMC may at any time recommend dose reduction or discontinuation of dosing for an individual subject or for all subjects (Section [9.1.5](#)). Regulatory authorities will be notified immediately if the study stopping criteria are met and study enrollment or dosing is halted.

Table 11: Clinical Criteria for Diagnosing Anaphylaxis

Anaphylaxis is highly likely when any one of the following 3 criteria are fulfilled:

1. Acute onset of an illness (minutes to several hours) with involvement of the skin, mucosal tissue, or both (eg, generalized hives, pruritus or flushing, swollen lips-tongue-uvula)
 
AND AT LEAST ONE OF THE FOLLOWING
 
a. Respiratory compromise (eg, dyspnea, wheeze-bronchospasm, stridor, reduced PEF, hypoxemia) b. Reduced BP or associated symptoms of end-organ dysfunction (eg, hypotonia [collapse], syncope, incontinence)

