7.7 Analysis of Primary Endpoints

The primary analysis endpoint is the incidence and severity of TEAEs, serious TEAEs, and related TEAEs in the SAD and RD Periods. The primary analyses will be based on Safety Analysis Set and displayed by analysis group in each period.

Adverse events will be coded by system organ class and preferred term using the Medical Dictionary for Regulatory Activities (MedDRA version 23.1 or above).

An AE (classified by preferred term) will be considered a treatment emergent adverse event (TEAE) if it occurred on or after the first dose of investigational product and was not present prior to the first dose, or it was present at the first dose but increased in severity or frequency. TEAE will be separately reported in SAD and RD Period.

Subject incidence of TEAEs and percentages will be tabulated as the following:

- TEAEs by analysis group in each period, SOC and PT (preferred term) (sorted by descending frequency in the pooled UX053 group by SOC and PT)
- Related TEAEs by analysis group in each period, SOC and PT (sorted by descending frequency by SOC and PT)
- Serious TEAEs by analysis group in each period, SOC and PT (sorted by descending frequency by SOC and PT)
- Serious Related TEAEs by analysis group in each period, SOC and PT (sorted by descending frequency by SOC and PT).
- TEAE by greatest severity, SOC and PT
- Deaths by analysis group in each period, SOC and PT (sorted by descending frequency by SOC and PT).
- TEAEs leading to discontinuation of study by analysis group in each period, SOC and PT (sorted by descending frequency by SOC and PT).

Detailed listings for all AEs, serious TEAEs, AEs leading to the discontinuation of study, AEs leading to the discontinuation of treatment, and death will also be generated.

The severity of all AEs will be based on Common Terminology Criteria for Adverse Events (CTCAE), Version 5.0, published on November 27, 2017, unless the AE is Cytokine Release Syndrome (CRS), in which case the AE will be graded by the American Society for Transplantation and Cellular Therapy (ASTCT) Consensus Grading for CRS ([Lee et al. 2019](#)). If an AE cannot be graded based on CTCAE, the investigator will assign a severity based on 1 = mild, 2 = moderate, 3 = severe, 4 = life threatening, and 5 = Death.

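### Appendix 1 asks for an adverse event's relationship to study drug but defines related to include research procedures, and the SAP tabulates related TEAEs without resolving the conflict

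*Protocol*

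**What the plan says.** Protocol Appendix 1 (Assessment of Causality) frames the judgement as being about the drug: "The causal relationship of all AEs to the study drug will be judged as either related" or not related. The guidance that follows widens it. Related means that "there is at least a reasonable possibility that the event is caused by the study drug or the research procedures". Not related means that "there is unlikely to be a reasonable possibility of a causal relationship between the event and study drug/IP or the research procedures", or that another condition is clearly the cause. Under Participation-emergent Adverse Events, the same appendix has events arising from study participation or specimen collection "noted as such in the case report form (CRF) as related to study intervention".

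Protocol 5.4.3 names such events as expected risks, among them "bruising from phlebotomy and local skin irritation from the continuous glucose monitor (CGM) or electrocardiogram (ECG) electrodes".

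On the analysis side, SAP 7.7 states: "The primary analysis endpoint is the incidence and severity of TEAEs, serious TEAEs, and related TEAEs in the SAD and RD Periods". It then lists tables of related TEAEs and of serious related TEAEs. It does not define related, does not exclude procedure-only events, and lists no table or listing for procedure-related events.

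**The concern.** The primary objective is the safety of UX053, and related TEAEs are one of the three components of its endpoint. A reader will take that table as the investigators' view of what the drug did. Under the Appendix 1 definitions it may also hold events that the investigator attributed only to a needle or an adhesive sensor.

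The appendix supports two readings, so coding may differ between sites even though this guidance is there to make causality assessments consistent. SAP Section 8 says that the study ended after 4 subjects in Cohort 1S and 4 in Cohort 2S, all open label. There is no placebo group to show the procedural background, so the causality call is the main separation of drug from study burden.

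The overlap also touches a risk of interest. Protocol 5.4.1 gives unusual bleeding or bruising as a possible sign of consumptive coagulopathy, and 5.4.3 gives bleeding and bruising as consequences of phlebotomy.

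**Working it through.** This is mainly a reading of text. The plan gives no figure that depends on it. The detection probabilities in Protocol 11.1 reproduce (1 − 0.8^6 = 73.8%, stated as 74%; 1 − 0.9^18 = 85.0%, stated as 85%) but do not bear on the definition.

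**Text side by side**

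- *Pointing to drug only:* the Appendix 1 lead-in; its supporting criteria (timing after IP, known response to IP, dechallenge and rechallenge with IP); Protocol 11.4, which reports by relationship to study drug; SAP 10.1.4, which names the variable as relationship to investigational product.
- *Pointing to drug or procedure:* both operative definitions in Appendix 1, and the instruction on participation-emergent events.
- *Reporting procedure events in their own right:* Protocol 11.4 asks for summaries, listings and narratives of procedure-related AEs.
- *Removing procedure-only events from the related-TEAE tables:* nothing in either document. SAP Section 1 gives the SAP precedence on analysis, but the SAP does not define related, so Appendix 1 governs by default.

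**Post-dose exposure to procedures.** Protocol Table 8 gives 10 PK time points to 24 hours, one of them pre-infusion, then Days 4, 7, 14, 21 and 28: 9 + 5 = 14 after the infusion starts. The glucose monitor is intended to be worn from Screening to Day 90 (Protocol Table 4). By the SAP 7.7 definition, only events that start or worsen after first dose count as TEAEs.

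**Weight of one subject.** One subject whose only related event is procedural moves the cohort rate by 1/4 = 25 percentage points and the pooled rate by 1/8 = 12.5 points.

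**Illustration under assumed rates.** Let q be the proportion of subjects with a post-dose procedure-only AE coded related. The documents give no value; 5% to 30% is assumed. With a true drug-related incidence of 20%, also assumed, and independence, the apparent related incidence is 1 − (1 − 0.20)(1 − q). The chance that at least one of the 8 subjects has such an event is 1 − (1 − q)^8.

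| q (assumed) | Apparent related incidence | Chance of at least one in 8 |
|---|---|---|
| 5% | 24% | 34% |
| 10% | 28% | 57% |
| 20% | 36% | 83% |
| 30% | 44% | 94% |

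Separating the two causes returns the incidence to the assumed 20%.

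**The case against.** The strongest reply is that the drug-only reading is the natural one. The lead-in, the supporting criteria and the closing note in Appendix 1 all speak of the drug or IP. A more likely alternative cause also supports a not-related call. An investigator could properly code a sampling bruise as not related. This stands: a reader might infer that every site must code such events as related, and the text does not support that. It supports only that sites may differ.

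A reader might also infer that procedural events cannot be told apart afterwards. That goes too far. Protocol 11.4 asks for them to be reported, Appendix 1 has them noted in the CRF, and SAP 7.7 tabulates by preferred term and lists all AEs, so with 8 subjects many would be recognisable. The CRF is not among the documents and may already hold separate fields. Even so, none of this takes the events out of the related-TEAE tables.

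The wording of Protocol 8.3.3, which pauses the study for serious Grade 3 or higher events "assessed as related to study drug or study procedures by the Investigator or Ultragenyx", does not contradict Appendix 1. It joins the two causes deliberately. Nor can symptoms from the controlled fasting challenge enter these data: that challenge is optional and confined to the repeat-dose cohorts.

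Finally, the analysis is descriptive, no test or threshold uses the related-TEAE rate, and any inclusion of procedure-only events overstates toxicity. This limits the importance of the point without removing it.

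**Conclusion.** The point holds as an internal inconsistency that reaches a component of the primary endpoint. Appendix 1 asks one question and defines the answer to another, and SAP 7.7 tabulates the result without saying which applies. Related and serious related TEAE tables therefore cannot be read with confidence as drug causality.

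The firm size is 25 percentage points per affected subject in a cohort of 4, provided that the subject has no other related event. The percentages in the table above rest on assumed rates, and on every counted procedure event being treatment-emergent and coded related; they show scale only. Whether any such event occurred is not known from the documents. Total TEAEs and serious TEAEs do not change.

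It is worth correcting because the correction is cheap and the dataset is small and uncontrolled. It does not invalidate the safety analysis.

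**What to change.** - **SAP 7.7:** define a related TEAE as one related to investigational product, for both the related and the serious related tables. Add a separate row or listing for procedure-related TEAEs, which also delivers what Protocol 11.4 asks for.
- **Appendix 1:** delete the reference to research procedures from both the related and the not-related definitions. For participation-emergent events, replace relation to study intervention with relation to study procedure.
- **CRF:** check whether drug and procedure causality are already recorded separately. If not, add the second field and query sites on the events marked related in the 8 treated subjects.
- **Protocol 8.3.3:** leave unchanged; it can draw on either answer.

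The cost is a few wording edits and, if needed, one CRF item and a small site query. As enrolment has ended, the SAP line and the query matter most for these data. The Appendix 1 edits matter mainly if its text is carried into another protocol.

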5.2. Overview of UX053 Development

A brief overview of existing information on UX053 is provided below; a comprehensive review of available data, including the structural components of UX053, detailed summaries of the nonclinical studies of UX053, and the potential risks and expected benefits of UX053, is contained in the Investigator's Brochure (IB). Information regarding the storage, handling, and administration of UX053 are provided in Section 9.1.

UX053 consists of an mRNA encoding full-length, human GDE encapsulated in a lipid nanoparticle (LNP), supplied in a sterile solution. CCI [REDACTED]

Intravenous (IV) administration of UX053 demonstrated improvement in GSD III disease manifestations in *Ag1* -/- mice and a dog model of GSD IIIa, both of which recapitulate features of human GSD III. Improvement of disease in these models was demonstrated by sustained reductions in glycogen content in the liver that correlated with increases in GDE protein. Glycogen reduction in skeletal muscles has been observed in GSD IIIa dogs treated with UX053, but only at a very low incidence and with minimal effect. It is hypothesized that a longer duration treatment will be necessary to show benefit in the muscle.

The PK characteristics of UX053, determined by measuring both *AGL* mRNA and ATX95, were evaluated in Sprague-Dawley rats and cynomolgus monkeys. Limited PK was also assessed in GSD IIIa and Beagle dogs. In all species, following a single 1-hour IV infusion of UX053, both *AGL* mRNA and ATX95 displayed a biphasic PK profile which can be generally characterized by a rapid distribution phase within the CCI [REDACTED] after the start of infusion and a slower terminal elimination phase with a longer half-life thereafter ($T_{1/2}$ in monkey: mRNA CCI [REDACTED] hours; ATX95 CCI [REDACTED] hours). Dose-dependent increases in *AGL* mRNA and ATX95 exposure were observed from CCI [REDACTED] mg/kg and CCI [REDACTED] mg/kg in rat and monkeys, respectively. CCI [REDACTED].

Toxicology studies in rats and cynomolgus monkeys indicated dose-dependent effects related to hepatic injury, coagulopathy, fibrinolysis, and complement activation, which are consistent with effects that have been reported for other siRNA or mRNA LNP therapies (Levin, 2019; Sabnis et al., 2018; Sedic et al., 2018; Henry et al., 2016).

[figure not shown]
This protocol is a FIH study; to date, no clinical investigations of UX053 have been conducted.

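### Appendix 1 counts a lack of prior data as a ground for calling an adverse event not related, with no rule for conflicting criteria; in a first-in-human study this may under-attribute effects that have no precedent

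*Protocol*

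**What the plan says.** Protocol Appendix 1 (Assessment of Causality) uses a two-level scale. Every adverse event is "judged as either related (which includes possibly, probably or definitely related) or not related (which includes unlikely or doubtfully related". Two bulleted lists follow, introduced by "To ensure consistency of AE and SAE causality assessments, Investigators should apply the following general guideline".

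- The related list includes plausible timing after dosing, a known or possible response to the product judged from preclinical or clinical data on it or on similar products, and no explanation from the disease or other treatment.
- The not-related list includes implausible timing, a more likely other cause and, as a separate bullet, "There are no data with the IP or similar products, suggesting the event occurs or may occur with the IP".

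No and/or rule joins the bullets in either list, and no rule ranks one list above the other.

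On the state of knowledge, Protocol 5.2 says: "This protocol is a FIH study; to date, no clinical investigations of UX053 have been conducted". Sections 5.4.1 to 5.4.1.2 nevertheless draw on toxicology in four species and on class effects of similar lipid-nanoparticle products.

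The investigator's call is used in several places. Related TEAEs are part of the primary endpoint (Protocol Section 6; SAP 4.1) and have their own tables (SAP 7.7). One of the eight pause criteria in Protocol 8.3.3 is a serious TEAE of Grade 3 or higher "that is assessed as related to study drug or study procedures by the Investigator or Ultragenyx". Protocol 9.1.5 allows dose reduction in the repeat-dose cohorts after a Grade 3 or higher TEAE that the investigator considers related, or after an intolerable TEAE.

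**The concern.** A first-in-human study exists partly to find effects that nobody predicted. For such an effect the not-related bullet is met simply because the drug is new. Suppose a subject has an unprecedented event soon after the infusion, with no other apparent cause. Two related bullets and one not-related bullet are met, and the appendix does not say how to decide. On a two-level scale with doubtful cases placed under not related, the bullet gives a written reason to choose that side.

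The investigator's call carries more weight here than it would in a controlled comparison. Protocol 7.1.3 relies on placebo to separate drug effects from GSD III events, but the single-dose cohorts are open label without placebo. SAP Section 8 limits the analysis to two of those cohorts, 1S and 2S. There is then no concurrent control against which to check an investigator's attribution.

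**Working it through.** **1. The plan's own figures.** The nearest figures are the detection probabilities in Protocol 11.1. The formula is P(at least one event) = 1 − (1 − p)^n.

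- n = 6, p = 0.20: 1 − 0.8^6 = 0.738, stated as 74%.
- n = 18, p = 0.10: 1 − 0.9^18 = 0.850, stated as 85%.

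Both reproduce. They concern any TEAE, so the causality bullet does not change them. No document gives a figure for related TEAEs or a rate of causality misclassification.

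**2. Which events meet the bullet.** It covers similar products as well as UX053, and the related list counts preclinical data.

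| Type of event | Prior data | Meets the bullet? |
|---|---|---|
| Hypersensitivity, hepatotoxicity, consumptive coagulopathy | Nonclinical and/or class data (5.4.1 to 5.4.1.2) | No |
| Class-type reactions such as rash, dyspnea, hypotension, headache | Class data (5.4.1.2) | No |
| Event with no nonclinical or class precedent | None | Yes |

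Only the last row is exposed.

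**3. How the lists resolve for that row.** Plausible timing and no other explanation point to related; lack of precedent points to not related. Nothing in Appendix 1 settles the conflict. If lack of precedent decides, the event leaves the related count. If timing decides, nothing changes. The bullet sits only in the not-related list, so it can lower the related count or leave it as it is; it cannot raise it.

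**4. What size could follow, by assumption only.** Let m be the share of truly drug-caused events called not related because of the bullet. The chance that at least one event is classified as related is 1 − (1 − p(1 − m))^n, treating subjects as independent with the same true incidence p. The values of m are assumed. The n = 8 row uses the 4 + 4 subjects in SAP Section 8.

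| n, p | m = 0 | m = 25% | m = 50% | m = 75% |
|---|---|---|---|---|
| 6, 20% | 73.8% | 62.3% | 46.9% | 26.5% |
| 18, 10% | 85.0% | 75.4% | 60.3% | 36.6% |
| 8, 20% | 83.2% | 72.8% | 57.0% | 33.7% |

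Worked case: n = 8, p = 0.20, m = 0.50 gives p(1 − m) = 0.10 and 1 − 0.9^8 = 0.570. For events with precedent, m from this source is zero. For unprecedented events it could lie anywhere from zero upwards.

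**5. Where the call matters and where it does not.**

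| Output or rule | Needs the investigator's relatedness call? |
|---|---|
| Related-TEAE tables (SAP 7.7) | Yes |
| Related serious Grade 3 or higher pause (8.3.3) | Investigator or sponsor can make it |
| Other seven pause criteria (8.3.3) | No; one liver rule requires that no plausible alternate explanation exists |
| Repeat-dose dose reduction (9.1.5) | Yes, unless the TEAE is intolerable |
| Infusion-related reactions (11.4) | No |
| All-TEAE and serious-TEAE tables (SAP 7.7) | No |

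**The case against.** The strongest reply is that the lists are guidance, applied with clinical experience and the Investigator's Brochure. The related category requires only a reasonable possibility and includes possibly related. A sensible investigator facing plausible timing and no other cause would call the event related, and the effect would be nil. This stands as a limit on size. It does not give the bullet a useful purpose.

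It can also be said that removing the bullet while keeping its positive counterpart is lopsided, given how many disease-related events and laboratory abnormalities the protocol expects. That carries less weight. A known precedent is informative; its absence says little about a drug not yet given to humans. Timing and alternative cause remain available for separating disease events.

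A reader might infer more than the documents support:

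- **That any new toxicity fits the bullet.** It does not. Similar-product data count, and the related list admits preclinical data, so a first human occurrence of a toxicity seen in animals or the class is not covered.
- **That related events are certainly under-counted.** Only the possible direction is known. The related list can point the other way.
- **That the bullet is circular with the SUSAR definition.** Expectedness is judged "as being serious and unexpected based on Reference Study Information", whereas the bullet asks whether any data suggest the event. An event can be unexpected and still have supporting data. The two texts are in tension for unprecedented events, not circular.
- **That "Negative de-challenge: the event does not improve after discontinuation of IP (when this information is available" wrongly clears lasting injuries after a single dose.** Its own qualifier answers this: after one infusion there is no dosing to stop, so the information is not available.
- **That safety surveillance depends on this call.** Appendix 2 requires all serious events to be reported within 24 hours whatever the cause, and most pause rules ignore relatedness.

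**Conclusion.** The point holds in a limited form. Appendix 1 lets absence of prior evidence count against causality, without a rule for conflict with the related list, in a study where human data did not exist. For events without nonclinical or class precedent this may lower the related-TEAE component of the primary endpoint. It may also lower the investigator's relatedness call for one pause criterion and for repeat-dose dose reduction. The last did not arise in the eight subjects analysed, who were in single-dose cohorts.

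The size is unknown and may be nil. The table of assumed m values shows sensitivity, not an estimate. A reader might take 1/8 = 12.5 percentage points per reclassified subject as the bias; that is only the step size of an incidence based on eight subjects, and it requires that the subject have no other related event. SAP 10.1.4 imputes missing causality as related, but this is a missing-data convention. It neither corrects a recorded not-related call nor contradicts the bullet.

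This is a cheap improvement worth making. It is not a defect that undermines the all-TEAE safety results.

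**What to change.** **In Appendix 1, and in any later protocol that reuses it:** delete the bullet on lack of prior data from the not-related list. Alternatively, keep it and add: *Absence of prior data with UX053 or similar products alone does not support a not-related assessment; an event with plausible timing and no more likely alternative etiology is assessed as related.* Leave the other bullets as they are.

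**In the study report, since enrolment has ended:** identify any TEAE recorded as not related whose assessment rested only on lack of prior data. Show related-TEAE incidence both as reported and with those events counted as related, labelled as a sensitivity analysis. Appendix 1 requires the causality assessment to be recorded but does not ask for its grounds, so this may need a query to sites. With eight subjects that is a small task.

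**Cost:** one bullet or one sentence, a few site queries and one extra table. Slightly more events will be recorded as related, so the related-TEAE figure may look a little less favourable.
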